10.6 End of Study Visit (Study Exit)

The study exit visit will occur when:

- the subject exits the study for any reason, including that all study wounds have healed; or
- The subject attends Visit 7.

Completion of end of study or appropriate forms is required.

11.1 Definitions

11.1.1 Adverse Event (AE).

An untoward medical occurrence, unintended disease or injury, or untoward clinical signs (including abnormal laboratory findings) in subjects, users or other persons, whether or not related to the investigational medical device and whether anticipated or unanticipated.

11.1.2 Serious Adverse Event (SAE).

An adverse event that results in one of the following outcomes:

- Death
- Serious deterioration in the health of the subject, users, or other persons as defined by one or more of the following:
 - a life-threatening illness or injury, or
 - a permanent impairment of a body structure or a body function including chronic diseases, or
 - in-patient or prolonged hospitalization, or
 - medical or surgical intervention to prevent life-threatening illness or injury, or permanent impairment to a body structure or a body function,
- Fetal distress, fetal death, a congenital abnormality, or birth defect including physical or mental impairment.

11.1.3 Adverse Device Effect (ADE)

An adverse device effect (ADE) is an AE related to the use of an Investigational Product. It includes AEs resulting from:

- Insufficient or inadequate Instructions for Use (IFU), deployment, implantation, installation, or operation,
- Any malfunction of the investigational medical device.
- Any event resulting from use error or from intentional misuse of the investigational medical device.

In this study, an investigational medical device is either of the randomised study dressings (AQUACEL® Ag+ Extra™ or Cutimed® Sorbact®).

11.1.4 Serious Adverse device Effect (SADE)

A serious adverse device effect (SADE) is an ADE that has resulted in any of the consequences characteristic of an SAE.

11.1.5 Unanticipated Serious Adverse Device Effect (USADE)

Serious adverse device effect, which by its nature, incidence, severity, or outcome has not been identified in the current version of the risk analysis report.

11.2 Adverse Events Categories and Relationship Determination

All AEs (regardless of relationship to the study procedures or severity) occurring from enrolment up to and including the subject's final study visit will be recorded by the Investigator. AEs may be either spontaneously reported to Investigator or elicited during questioning and examination of a subject. All identified AEs must be recorded in the patient record and on the Adverse Event case report form. If known, the diagnosis of the underlying illness or disorder should be recorded, rather than its individual symptoms.

11.3 Categories of Severity

The following definitions will be used for the categories of "Severity":

- Mild: awareness of sign or symptom, but easily tolerated
- Moderate: discomfort enough to cause interference with usual activity
- Severe: incapacitating, with inability to work or do usual activity

11.4 Relationship to Investigational Device

Causality assessment is required for AEs and SAEs that occur during clinical investigations. There is currently no standard international nomenclature to describe the degree of causality or relatedness of an AE with the Investigational Product. The following terms will be used during this study:

Related - The AE is directly and clearly related to the Investigational Product.

Possibly Related - There is a reasonable likelihood that the AE is due to the Investigational Product, as evidenced by the following:

- There may be temporal association with the Investigational Product (e.g., within 24 hours of device placement).
- The AE, or level of severity of the AE, is unlikely to be explained by other etiologies (known to be related to the study disease, Subject's baseline medical condition, or concomitant medication).

Not Related - The AE is definitely not related to the Investigational Product, or the AE is unlikely to be related to the Investigational Product because of a lack of temporal association or is known to be related to one or more of the following:

- Morbidity associated with underlying medical condition.
- Treatment procedure.
- Concomitant medication.
- A relationship to the Investigational Product is not biologically plausible.

11.5 Procedure for Monitoring and Recording of Serious Adverse Events

All SAEs occurring after from enrolment up to and including the subject's final study visit will be reported. All SAEs must be followed until the event no longer meets serious reporting criteria, resolves, stabilizes, or the subject is considered lost to follow-up.

All SAEs that occur during the collection period must be reported by the Investigator and/or their appointed Designee within 24 hours of first becoming aware of the occurrence of the SAE. Reports should be submitted to the responsible monitor and Convatec Safety & Compliance on an Initial SAE Report (SAER) form provided by Convatec Ltd. Available supporting documentation, if applicable, (e.g., discharge summary, laboratory reports) should be included. Personal identifiable information will be

deleted, and the subject number will be written on the report. All attempts should be made by the Investigator to follow the progress of the SAE.

Serious adverse events will be listed as a single diagnosis (e.g., septic shock, flu-like syndrome) or a single event (e.g., headache, bone pain) whenever possible. Each single event, even if concurrent, should be reported on separate SAE Form.

Convatec Ltd. has the responsibility to expeditiously review and report all SAEs to comply with regulatory requirements. Where applicable, Convatec Ltd. must:

- Report the SAE or SADE to the Lead Investigators at each site.
- Report the SAE or SADE to the appropriate regulatory authorities in accordance with local requirements.
- Ensure that Competent Authorities and all responsible IRB/Ethic Committees are notified of the events in the appropriate timeframe in accordance with local requirements.

If deemed appropriate (e.g. SADE) Convatec will update the Risk Assessment accordingly.

11.6 Safety Reporting Timelines

Type of Event	Report to Sponsor	Method
Adverse Event	Per Protocol Visit	Complete eCRF
Adverse Device Effect	Per protocol visits	Complete eCRF
SAE	Within 24 hours of study staff becoming aware of event	Initial: phone/email to sponsor Followed by: Complete CRF
SADE	Within 24 hours of study staff becoming aware of event	Initial: phone/email to sponsor Followed by: Complete CRF
USADE	Within 24 hours of study staff becoming aware of event	Initial: phone/email to sponsor Followed by: Complete CRF

11.7 Follow-Up Information for Serious Adverse Events

Subsequent or new information will be submitted by the site staff to the Sponsor or its designee, in the form of an updated Adverse Event Report Form. Personal identifiable information will be deleted/blacked out and the subject number will be written on the report. Every attempt should be made to obtain follow-up SAE information. All unresolved SAEs for subjects considered lost to follow up should be documented appropriately in source documentation and reported to Convatec Ltd. on a follow-up form.

11.8 Device Deficiency

A device deficiency is an inadequacy of a medical device with respect to its identity, quality, durability, reliability, safety, or performance. This may include malfunctions, use errors, and inadequacy in the information supplied by the manufacturer including labelling. This definition includes device deficiencies related to the investigational medical devices or to a comparator, i.e., a medical device, therapy (e.g., active treatment, normal clinical practice), placebo or no treatment, used in the control group in a clinical investigation (ISO 14155:2020). Device deficiencies may occur before use, during use, or after use. All Investigational Product deficiencies will be collected throughout the study and captured on the Device Deficiency eCRF. Any treatment delay that was caused by the device deficiency will be collected as well if the device will be returned to the Sponsor.

The Investigator is responsible for assessing the reportability of each event, and submitting the Device Deficiency Report when the deficiency meets the following criteria:

- Any device deficiency that led to an SAE (the PI must submit both an SAE Report and the associated Device Deficiency Report to the Sponsor/designee).
- Any device deficiency that might have led to an SAE if any of the following is true.
 - Suitable action had not been taken.
 - Intervention had not been made.
 - Circumstances had been less fortunate.

The PI must submit the Device Deficiency Report to the Sponsor as soon as possible, but not later than 5 business days, following the date of awareness of the event. The PI is responsible for reporting the device deficiency to the ethics committee, if required per ethics committee regulations.

The Sponsor will promptly evaluate the report to determine further actions. When applicable, appropriate Corrective and Preventive Actions (CAPAs) will be taken to protect the safety of Subjects, users, and other persons. The Sponsor will arrange for the safe return of the Investigational Product that is subject to a Device Deficiency.

12 PROTOCOL DEVIATIONS

Except for a change that is intended to eliminate an immediate hazard to the subjects, the approved protocol shall be conducted as described. Any significant protocol deviation must be documented. Every deviation recorded on Deviation Form will be evaluated for its impact.

12.1 Deviation Reporting Timelines

Type of Deviation	Report to Sponsor	Method
Subject safety, rights, OR welfare; OR data integrity; OR compromise the statistical analysis of the study; OR Lack of Informed Consent; OR Inclusion/Exclusion Criteria	Within 24 hours of study staff becoming aware of event	Initial: phone/email to sponsor Followed by: Complete CRF
All other protocol deviations	Per protocol visits	Complete CRF

13 PREMATURE TERMINATION, SUSPENSION OR ROUTINE CLOSE-OUT OF THE STUDY

13.1 Premature Termination or Suspension

Convatec may suspend or prematurely terminate a clinical investigation for significant and documented reasons or for no reasons or if requested by regulatory authorities.

Convatec may terminate or suspend the participation of a site or investigator if the monitor and/or auditor identify serious or repeated deviations on the part of an investigator. If the suspension or premature termination occurs, Convatec shall justify its decision in writing and promptly inform the Investigator and IRB/Ethics Committee.

If suspension or premature termination occurs,

- Convatec will remain responsible for providing resources to fulfil the obligations of the study and existing agreements
- The investigators or authorised designee will inform the enrolled subjects, if appropriate

13.2 Procedure for resuming the clinical investigation after temporary suspension

When the analysis of the reason for the suspension is complete, the corrective actions are implemented and the decision to lift the suspension reached, Convatec will inform the investigator and ethics committee of the rationale.

13.3 Routine Close-Out

Routine close out activities shall be conducted to ensure that the investigator records are complete, all documents needed for Convatec's files are retrieved and previously identified issues have been resolved and all parties are notified.

Within 90 days after the closure of the study Convatec will notify the Ethics Committee of the end of the study. Within 1 year after the end of the study, the final report will be submitted to the Ethics Committee.

14 MONITORING

Study Monitoring is conducted to ensure that the rights, safety, and well-being of study participants are protected, that the reported study data are accurate, complete, and verifiable, and that the conduct of the study is in compliance with the currently approved protocol, GCP, and with applicable regulatory requirements.

Convatec is responsible for ensuring the proper conduct of the clinical investigation with regard to protocol adherence and validity of the data recorded on the CRFs. Convatec has assigned study monitor(s) to this clinical investigation. The progress of the clinical investigation will be monitored by:

- Periodic and/or remote review
- Telephone communications
- Review of CRFs and source documentation (e.g., subject records)

The study monitor(s), other authorized representatives of the Sponsor, representatives of the IRB/EC, or regulatory authorities may inspect all documents and records required to be maintained by the Investigator, including, but not limited to subject records for the participants in this study. The clinical study site will permit access to such records. The Investigator will give Convatec study monitor(s) direct access to source documents that support data on the CRFs. This includes electronic records.

Investigator non-compliance of required study responsibilities will require Sponsor sanctions to alleviate the non-compliance, including corrective and preventative actions up to and including disqualification of the Investigator/Site.

Details of the clinical site monitoring are documented in a Monitoring Plan (MP), which will be written prior to the first monitoring visit. The MP describes in detail who will conduct the monitoring, at what frequency monitoring will be done, at what level of detail monitoring will be performed, and the distribution of monitoring reports.

Independent audits may be conducted by Convatec or designee to ensure monitoring practices are performed consistently across all participating sites and that monitors are following the MP.

Any Monitoring Visits will comply with the Government restrictions on travel due to the Covid-19 pandemic, if applicable.

15 DEVICE ACCOUNTABILITY

Investigative sites will use formulary/on-the shelf inventory for treatment of the subjects with AQUACEL® Ag+ Extra™ and Cutimed® Sorbact®. The sponsor will not provide any products. Therefore, device accountability is not required.

16 CONFIDENTIALITY

Participant confidentiality and privacy is strictly held in trust by the participating Investigators, their staff, the Sponsor, and their authorised representatives. This confidentiality is extended to cover testing of biological samples and genetic tests in addition to the clinical information relating to participants. Therefore, the Clinical Investigational Plan, documentation, data, and all other information generated will be held in strict confidence. No information concerning the study, or data will be released to any unauthorized third party without prior written approval of the Sponsor. All research activities will be conducted in as private a setting as possible.

Study data, which is for the purposes of statistical analysis and reporting, will be transmitted to and stored at Convatec or an approved supplier. This will not include the participant's contact or identifying information. Rather, individual participants and their research data will be identified by a unique study identification number. The electronic data capture system used by clinical sites and by Convatec research staff will be secured and password protected.

17 DATA HANDLING AND RECORD KEEPING

Data collected for this study will be analysed and stored at Convatec or an approved supplier for use by researchers, including those outside of the study. Permission to transmit, store and use data outside of the study will be included in the informed consent.

17.1 Data Collection and Management Responsibilities

Data collection is the responsibility of the clinical study staff at the site under supervision of the site Investigator. The Investigator is responsible for ensuring the accuracy, completeness, legibility, and timeliness of the data reported.

All source documents should be completed in a neat, legible, permanent, and un-editable manner to ensure accurate interpretation of data. Data recorded in the electronic case report form derived from source documents must be consistent with the data recorded on the source documents.

Data will be entered into a compliant data capture system provided by Convatec. The data system includes password protection and internal quality checks, such as automatic range checks, to identify data that appear inconsistent, incomplete, or inaccurate.

17.2 Study Records Retention

The study participant's information will be securely stored at each clinical site for internal use during the study. At the end of the study, all study records will continue to be kept in a secure location for as long a period as dictated by the reviewing IRB/EC, Institutional policies, regulatory authorities, or Sponsor requirements.

No records will be destroyed without the written consent of the Sponsor. It is the responsibility of the Sponsor to inform the Investigator when these documents no longer need to be retained.

17.3 Sponsor Oversight

Routine review of submitted study information by the Sponsor will be conducted to ensure Protocol compliance. Items reviewed include, but are not limited to: adverse events, deviations, number of withdrawn / terminated subjects; which all may impact completion of the study. Appropriate measures may be taken to ensure Investigator compliance with the Protocol.

18 STATISTICAL CONSIDERATIONS

This study is a multi-center, prospective, parallel, concurrent RCT. Details of the statistical analysis will be described in the SAP. This section provides key elements of the statistical approach.

18.1 Alpha Value

Alpha value will be 0.05 for both one-way and two-way testing.

18.2 Statistical Approach for the Primary Endpoint

The study hypothesis is that the Experimental Treatment with AQUACEL® Ag+ Extra™ will have similar effectiveness to the Control Treatment with Cutimed® Sorbact® in proportion of wounds that have completely healed by 84 days. The statistical hypothesis is that Experimental Treatment with AQUACEL® Ag+ Extra™ will be non-inferior to Control Treatment with Cutimed® Sorbact® in proportion of wounds that have completely healed by 84 days.

The statistical null and alternative hypotheses are as follows:

$$\begin{aligned} H_0: \pi_{Exp} - \pi_{Con} &\leq \delta \\ H_A: \pi_{Exp} - \pi_{Con} &> \delta \end{aligned}$$

where π_{Exp} and π_{con} represent the true proportion of target wounds that have healed by 84 days in patients treated with AQUACEL® Ag+ Extra™ and Cutimed® Sorbact®, respectively, and δ is the non-inferiority margin. The non-inferiority margin (δ) is set to -15%.

The statistical definition of success is the rejection of H_0 . The null hypothesis (H_0) will be tested by constructing a two-sided 90% confidence interval for the difference in the proportions of ulcers that have completely healed between the Experimental Arm and the Control Arm. If the lower boundary of the interval does not include δ , then the null hypothesis will be rejected. If non-inferiority of AQUACEL® Ag+ Extra™ to the Cutimed® Sorbact is demonstrated, its superiority will be tested.

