1 BACKGROUND & JUSTIFICATION

The burden of chronic wounds

Caring for patients with acute and chronic wounds represent a significant challenge on healthcare systems and societies around the world. Real-world data from the UK (2017/2018) has shown that the total costs to the UK health system of caring for patients with wounds was around GBP£8.3BN per year.¹ This is equivalent to the UK spend on systemic diseases such as osteoarthritis and rheumatoid arthritis which was GBP£10.2 billion in 2017/2018. Whilst 89% of acute wounds heal within a year, just 49% of chronic wounds close within the same period. Whilst the understanding of how to treat chronic wounds has improved over time, the increased age of the population and their attendant co-morbidities means that healing rates don't appear to have improved.^{1,2}

The significance of venous leg ulcers

One of the most prevalent chronic wounds are venous leg ulcers (VLU). In Germany, about 0.6–1% of the population are diagnosed with a VLU, with the prevalence in people above the age of 60 being much higher (3.9%). VLU are wounds on the lower extremity resulting from venous hypertension and hypervolemia. The pooling of venous blood gives rise to oedema which leads to poor perfusion and tissue breakdown. The mainstay of conservative treatment is compression therapy to counteract the oedema and assist venous return. Many VLU are in fact mixed ulcers as patients often have a degree of arterial disease.³ Only about half of VLUs heal within 4 months, leaving a significant proportion of non-healing ulcers to place a burden on health resources and patient quality of life. Improvements in healing of VLU would have a significant impact.

The importance of bacteria and infection in chronic wounds

Much of the present day understanding of the clinical interventions required to improve healing in chronic wounds is enshrined in the widely used concept of Wound Bed Preparation (WBP).⁵⁻⁸ Several derivations and additions to the TIME principles have since been developed.⁹ The key concept at the heart of the WBP scheme is to break the clinical problem down into a series of interconnected barriers to intrinsic healing. The barriers are grouped into 4 areas: Tissue; Infection/Inflammation; Moisture/Exudate; Edge/Epithelialisation: the so called “TIME” paradigm.

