9.4 Enrolment of Subject with Multiple Wounds

Subjects with multiple wounds are allowed into study. Each wound that meets all wound-specific inclusion and none of the wound-specific exclusion criteria should be enrolled into study. The randomization occurs at the subject level. All study wounds for a specific subject will be treated with the same study device (e.g., all study wounds in a subject randomized to AQUACEL® Ag+ Extra™ will be treated with AQUACEL® Ag+ Extra™. No wound-level cross-over is allowed.

TABLE 9.3-1: Schedule of Events

	Visit 1 Day 1	Visit 2 Day 14 (+/- 2 days)	Visit 3 Day 28 (+/- 2 days)	Visit 4 Day 42 (+/- 2 days)	Visit 5 Day 56 (+/- 2 days)	Visit 6 Day 70 (+/- 2 days)	Visit 7 Day 84 (+/- 2 days)	Additional Visit	End of Study Visit [^]
Informed Consent	X								
Inclusion / Exclusion	X								
Demographics	X								
Medical History	X								
Concomitant Medication	X	X	X	X	X	X	X		X
Wound History	X								
Wound-QoL-14	X	X*	X*				X		X@
Wound debridement per usual practice	X	X	X	X	X	X			
Wound Assessment	X	X	X	X	X	X	X	X	X
Randomisation	X								
Decision to continue with randomised dressing or Standard of Care		X							
Randomised Dressing Application	X	X	X\$	X&	X&	X&			
Secondary Dressing Application#	X	X	X	X	X	X			
Apply compression therapy	X	X	X	X	X	X			
Adverse Events	X	X	X	X	X	X	X	X	X
Device Deficiency%	X	X	X	X	X	X	X	X	X

* Wound-QOL-14 will be completed following the completion of treatment with randomized dressing on Day 14 (+/- 2 days) or on Day 28 (+/- 2 days) if additional 14 days of treatment with the randomised dressing occurred.

@ Collect QOL-14 if the Additional Visit is Study Completion visit.

\$ Application of the randomised dressing after Visit 2 (14-day visit) at the discretion of the investigator.

& After day 28, the PI or delegate will continue treatment of the wound according to the clinical needs based on their evaluation of the wound. If an antimicrobial wound dressing is required, the dressing that was randomly assigned during the initial phase of the study can continue to be used

Secondary dressing to be applied at the discretion of the investigator.

% If applicable

^ If end of study visit is not Visit 7

10 Visits

After Informed Consent has been obtained, the following study procedures will be performed.

10.1 Visit 1: Screening and Baseline: Day 1

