The following procedures and data are collected at Visit 1. All information on this visit is required. Missing data and assessments will be considered a protocol deviation.

- Obtain Informed Consent
- Inclusion and Exclusion Criteria Review and Documentation
- Demographics (Sex, Age, Height, Weight, BMI calculation, Ethnicity)
- Medical History (Cardiovascular, Respiratory, Gastro-Intestinal, Endocrine, Haematological, Musculo-skeletal, Neoplasia, Neurological, Immunological, Dermatological, Allergies, Psychological, and Other)
- Obtain Concomitant Medications (Medication Used, Route, Dose, Unit, Frequency, Indication, Start Date, Stop Date or Ongoing)
- Study Wound(s) Assessment
 - Duration of wound
 - Location of the wound (i.e., left/right leg, posterior/ anterior, medial/ lateral, etc.)
 - Wound size (measured in cm at the longest point and across the widest point)
 - Wound bed appearance
 - Exudate level, colour, and consistency
 - Condition of peri-wound skin
 - Maximum pain level on a scale of 0 to 10 within the last 24 hours
 - Level of odour on a scale of 0 to 10 for the study participants and mild/medium/strong for the clinician.
 - Therapeutic Index for Local Infections (TILI) score
- Wound-QoL-14
- Randomisation to either AQUACEL® Ag+ Extra™ or Cutimed® Sorbact®
- Randomised dressing application (Size and Lot Number)
- Apply compression per standard of care (documentation of type used)
- Documentation of the use of secondary dressings, if applicable

Each study wound in subject with multiple study wounds is assessed independently.

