18.4 Sample Size Determination

Under the assumption that the proportion of completely healed ulcers by day 84 is 0.8 (80%), the sample size of 206 subjects and minimum of 206 wounds randomized 1:1 to Experimental and Control arms will have 85% power to reject the null hypothesis.

Sample size assumptions concerning the proportion variance and average number of wounds per subject will be verified during the study in a blinded fashion. Such verification does not inflate alpha-value.

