18.6 Randomisation

Subjects will be randomised on a 1:1 basis to either the AQUAUCEL® Ag+ Extra™ or Cutimed® Sorbact® dressing at the subject level. All wounds for the same subject will be treated using the randomised dressing. The randomization sequence will be stratified by study centre. Other details concerning the randomization are described in the Randomisation Plan.

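### The primary risk difference in section 18.2 is unadjusted as written; pre-specifying adjustment for baseline ulcer area, wound duration and country would add power at little cost if area and duration predict closure

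*Combined protocol and SAP*

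**What the plan says.** Section 18.2 defines the primary test as "a two-sided 90% confidence interval for the difference in the proportions of ulcers that have completely healed", compared with a margin of -15 percentage points. It names no covariate, stratum or model, and no other section in the combined document does.

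Three other places bear on the choice:

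- **Randomisation (18.6).** "The randomization sequence will be stratified by study centre". Area and duration are not stratification factors.
- **Baseline data (10.1, Visit 1).** Wound duration is recorded, and so is size: "Wound size (measured in cm at the longest point and across the widest point". All Visit 1 items are compulsory: "Missing data and assessments will be considered a protocol deviation".
- **Unit of analysis (9.4).** "Subjects with multiple wounds are allowed into study". Randomisation is by subject, while the endpoint is counted by wound.

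Section 18 gives only the main features and adds: "Details of the statistical analysis will be described in the SAP". No SAP text is included. Section 18.4 bases its power on "the sample size of 206 subjects and minimum of 206 wounds randomized 1:1", with 80% healed by day 84.

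**The concern.** Section 6.1 admits ulcers from 1 to 100 cm2 and from 60 days to 18 months old. If area and duration predict closure across that range, they account for part of the outcome variance. An unadjusted difference leaves that part in the standard error. It also leaves any chance imbalance in area or duration uncorrected, since neither is a stratification factor.

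The spare precision matters because the design has little slack. Section 18.4 states no dropout allowance and section 8.1 says that subjects who leave are not replaced. The 80% healing assumption sits beside a general statement in section 1: "Only about half of VLUs heal within 4 months". If healing is nearer 50%, the variance of the difference rises and power falls well below 85%.

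Timing matters too. The trial is open label (section 3.1), so covariates chosen once outcomes are visible could be challenged as selective.

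**Working it through.** **Inputs from the documents.** 103 subjects per arm (206 randomised 1:1, 18.4); healing p = 0.80 (18.4), taken as equal in both arms; margin 0.15 (18.2); one-sided alpha 0.05, matching the two-sided 90% interval (18.1, 18.2), so z = 1.6449. p = 0.50 is used as a stress case, prompted by section 1.

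**Input assumed.** R2, the share of outcome variance explained by the baseline covariates. The documents give no figure, so 0 to 0.20 is shown.

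**Step 1: reproduce the stated power.** Power = Phi(0.15 / SE - 1.6449), with SE = sqrt(2p(1-p)/103).

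- p = 0.80: SE = sqrt(0.32/103) = 0.0557; 0.15/0.0557 = 2.691; 2.691 - 1.645 = 1.046; power 85.2%. The stated 85% is right for an unadjusted difference with one wound per subject and no dropout.
- p = 0.50: SE = sqrt(0.50/103) = 0.0697; 0.15/0.0697 = 2.153; 2.153 - 1.645 = 0.508; power 69.4%.

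**Step 2: adjust.** Multiply the variance by (1 - R2).

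| R2 | Power, p = 0.80 | N for 85% power, p = 0.80 | Power, p = 0.50 |
|---|---|---|---|
| 0 | 85.2% | 206 | 69.4% |
| 0.05 | 86.8% | 196 | 71.4% |
| 0.10 | 88.3% | 186 | 73.4% |
| 0.20 | 91.4% | 164 | 77.7% |

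At p = 0.80, an assumed 10% loss reduces unadjusted power to 81.8%. R2 = 0.10 restores 85.2%, because the factors 0.9 and (1 - 0.10) cancel.

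**Step 3: simulate the proposed estimator.** Logistic model, standardised to a risk difference, with standard errors summed by subject. There were 8,000 trials per scenario for power (true difference 0) and 8,000 for error (true difference -15 points). Assumed: 15 unequal centres (3 to 30 subjects) in 3 countries, blocks of 4 within centre, centre SD 0.4 on the logit scale, log area uniform over 1-100 cm2, and duration uniform over 2-18 months. Subjects had either one wound each, or 20% had two wounds with a subject random intercept of SD 1. Monte Carlo SE is 0.3-0.5 point for power and about 0.24 for error.

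Power (%), unadjusted to adjusted:

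| Scenario | R2 0 | R2 0.10 | R2 0.20 |
|---|---|---|---|
| 80% healed, one wound each | 85.2 to 84.9 | 86.2 to 88.9 | 85.9 to 92.7 |
| 80% healed, 20% with two wounds | 88.8 to 88.4 | 89.4 to 92.0 | 90.5 to 94.9 |
| 50% healed, one wound each | 68.6 to 68.6 | 68.6 to 73.2 | 69.3 to 77.5 |
| 50% healed, 20% with two wounds | 74.6 to 74.1 | 75.0 to 78.0 | 74.5 to 82.5 |

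One-sided error over these 12 scenarios was 4.3-5.4% adjusted and 4.2-5.2% unadjusted. Country alone changed power by 0.3 point or less. The model failed to converge in at most 0.2% of trials.

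**Step 4: repeat independently, one wound each.** With 2,500 trials per scenario, power at R2 of 0, 0.10 and 0.20 went from 85.8 to 86.0, 85.7 to 88.7 and 84.9 to 90.9 at 80% healing. At 50% it went from 68.4 to 69.2, 70.8 to 74.8 and 68.4 to 77.6. Error was 4.7-5.5% adjusted and 4.5-5.3% unadjusted. Another run of 3,000 trials per scenario, with normally distributed covariates, gave error of 4.7-5.9% adjusted and 4.4-6.1% unadjusted (Monte Carlo SE about 0.4 point). Adjustment did not materially change the error rate in any run.

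**The case against.** The strongest reply is that nothing is wrong. The unadjusted interval is a valid test, 206 reproduces, and covariates are the kind of detail that section 18 leaves to the SAP. That stands: this is an improvement, and the SAP may already contain it.

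The gain also rests on an R2 that the documents do not give. That stands too, and the upper end is demanding. In a logistic model with equal effects of log area and duration, R2 = 0.20 at 80% healing needs an AUC of about 0.80, with roughly 40% healing in the worst-prognosis tenth and 98% in the best. R2 = 0.05 needs an AUC of about 0.66 and gains 1.6 points.

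The centre stratification is not a source of power here. Country added almost nothing, and a centre-level term was not simulated. Section 5 allows further countries, so the 3 countries and 15 centres are assumptions. The simulation also did not cover missing outcomes or a misspecified covariate model.

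Finally, 50% healing questions the 80% assumption more than the estimator, and section 18.4 plans a blinded check of the variance and of wounds per subject. But 18.4 states no action if that check disappoints. Adjustment is only a partial remedy: with one wound each and R2 = 0.20, power at 50% healing is still about 77.5%.

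None of this removes the case for adjusting. The data are already compulsory, error is held, and the loss if the covariates are useless is at most 0.5 point in simulation.

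**Conclusion.** The point holds as a recommended efficiency improvement. Section 18.2 as written leaves compulsory baseline information unused. By formula, adjustment raises power at 206 subjects by 0 to 6.1 points at 80% healing (91.4 - 85.2 before rounding) and by 0 to 8.3 points at 50% (77.7 - 69.4), for R2 between 0 and 0.20. Nearly all of it comes from area and duration. Confidence is medium, because R2 is assumed and the SAP is not available to read. The stated 85% power is correct and needs no change.

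**What to change.** In section 18.2, or in the SAP with a reference from 18.2, fix the following before outcomes are seen:

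- **Primary estimator:** a wound-level risk difference standardised (g-computation) from a logistic model with arm, log baseline area (length x width), wound duration and country. Pool centres to country and use no separate centre indicators.
- **Inference:** standard errors clustered by subject with the n/(n-p) correction, and a two-sided 90% interval against the same -15-point margin. Standardisation keeps the risk-difference scale; a conditional odds ratio would not test this margin.
- **Fallback:** the unadjusted clustered interval if the model does not converge.
- **Missing baseline values:** median imputation without reference to arm.
- **Supportive analysis:** the unadjusted interval.

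If the SAP already specifies an adjustment, cite it in 18.2 and check it against these items. The cost is a little programming and a short paragraph of rules, with no new data collection.
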